Participants will be taught to give themselves rIL-2 injections. This will require substantial clinician support in terms of both time spent instructing participants and in availability to answer participant questions and respond to participant concerns about injections and side effects. Refer to the Manual of Operating Procedures (MOPS) document for further details on initial and subsequent dose administration

C.5.2. Guidelines for Dosage Modification

Participants will be monitored closely for side effects of rIL-2. Participants who experience dose-limiting side effects may have their rIL-2 temporarily interrupted or their dose reduced.

The Manual of Operations (MOPs) includes a list of toxicities for which the investigator may choose to temporarily interrupt or dose-reduce rIL-2 (hereinafter, dose-limiting toxicities). An outline of criteria for certain specific potential adverse events are provided in section E.1. Briefly, the following guidelines apply:

- For toxicities during the 4-consecutive-day administration of rIL-2 that are considered dose-limiting, the remaining rIL-2 doses of that cycle of therapy will be interrupted until the dose-limiting toxicity is no longer considered dose-limiting.
- In some circumstances, a toxicity may be regarded as dose-limiting in the opinion of the investigator, even if it does not meet the above-mentioned criteria. In these instances, the clinical judgment of the investigator takes precedence.
- When rIL-2 treatment is reinitiated after interruption because of a dose-limiting toxicity, the dose will be reduced by up to 1.5 MIU per injection (3 MIU/day). If the reduced dose results in a dose-limiting toxicity during the same cycle, rIL-2 therapy will again be interrupted. Further dose reduction, if necessary, will be made in the same fashion.
- If a participant cannot tolerate an rIL-2 dose of 2 MIU twice a day then rIL-2 therapy will be permanently stopped.
- If, after a dose reduction, a participant completes a treatment cycle without significant toxicity, then escalation of the rIL-2 dose at the next cycle may occur by an increment of up to 1.5 MIU/dose (3 MIU/day).
- The total duration of a course of rIL-2 will not be extended for doses missed as a result of toxicity or any other reason.

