E.1. MANAGEMENT OF SPECIFIC ADVERSE EVENTS

The Guidelines for Dose Modification, (protocol section C.5.2), apply to all of the scenarios listed in this section.

E.1.1. Serious Infections

All subjects will be monitored for signs or symptoms of a serious or local infection at each visit. All subjects who develop a serious infection while on study will be referred for immediate medical care to a qualified healthcare professional. Participants who develop any of the following infectious events will be required to discontinue study treatment:

- Tuberculosis, pulmonary or extrapulmonary
- Non-tuberculous mycobacterial infection, disseminated or extrapulmonary
- *Pneumocystis jirovecii* pneumonia
- Coccidioidomycosis, disseminated or extrapulmonary
- Cryptococcosis, extrapulmonary
- Cryptosporidiosis or isosporiasis, chronic intestinal (greater than 1 month's duration)
- Cytomegalovirus disease (other than liver, spleen, or lymph nodes) and including retinitis with loss of vision
- Histoplasmosis, disseminated or extrapulmonary
- Kaposi's sarcoma
- Lymphoma, Burkitt's or immunoblastic, regardless of anatomical location
- Lymphoma, primary of brain
- Progressive multifocal leukoencephalopathy
- Toxoplasmosis of brain
- Herpes zoster reactivation involving more than one dermatome or visceral involvement including but not limited to viral pneumonia, encephalitis and hepatitis.
- Any serious infection that is considered life-threatening or requires inpatient treatment. Participants who experience other serious infections not listed above that do not require inpatient treatment and are not considered life-threatening will have study treatment temporarily stopped until the infection is controlled. These subjects may restart study drug once the infection is controlled.

Other infections, including local infections, will also require referral to qualified medical treatment. The study principal investigator, in consultation with the SMC if necessary, will determine if an infection not listed above warrants permanent treatment discontinuation.

E.1.2. Acute Hypersensitivity Reactions

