To minimize the risk of a severe, immediate-type hypersensitivity reaction or capillary leak syndrome, the first dose of study agent will be administered in the Special Immunology Unit by personnel with experience administering rIL-2 to over 50 participants in the SILCAAT and ACTG 328 trials. Participants will be monitored for a minimum of 30 minutes following the first dose of study drug by personnel with life support training and access to adequate life support equipment and resuscitation medication.

Development of a grade ≥ 3 hypersensitivity reaction, a grade 2 hypersensitivity reaction that includes manifestations of angioedema, or suspected or confirmed capillary leak syndrome will require permanent treatment discontinuation.

E.1.3. Neutropenia

Participants who develop neutropenia will be referred for treatment by a qualified healthcare professional. Volunteers with an ANC $< 2,000$ cells/mm 3 at screening will be excluded.

- Should the ANC decrease to ≥ 500 but $\leq 1,000$ cells/mm 3 , the rIL-2 dose will be interrupted until the ANC is $> 1,000$ cells/mm 3 and then rIL-2 will be restarted at 3.5 million units twice daily. If the ANC then remains above 1,000 cells/mm 3 , this dose will be continued until the end of study.
- If the ANC drops to ≥ 500 but $\leq 1,000$ cells/mm 3 while on the reduced dose of 3.5 million units twice daily, rIL2 will be discontinued until the ANC reaches 1,000 cells/mm 3 , and then resumed at a dose of 2 million units twice daily. If the ANC then remains above 1,000 cells/mm 3 , this dose will be continued until the end of study. If the ANC falls again to $\leq 1,000$ cells/mm 3 while on the reduced 2 million unit twice daily dose, rIL2 will be permanently discontinued.
- Should the ANC decrease to < 500 cells/mm 3 , rIL-2 will be permanently discontinued.

E.1.4. Thrombocytopenia

Participants who develop thrombocytopenia will be referred for treatment by a qualified healthcare professional. Volunteers with platelet counts $< 150,000$ /mm 3 will be excluded.

- Should the platelet count decrease to $\geq 50,000$ but $\leq 100,000$ /mm 3 the rIL-2 dose will be interrupted until the platelet count is $> 100,000$ /mm 3 and then rIL-2 will be restarted at 3.5 million units twice daily. If the platelet count then remains above 100,000 /mm 3 , this dose will be continued until the end of study.

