- If the platelet count drops to $\geq 50,000$ but $\leq 100,000$ /mm 3 while on the reduced dose of 3.5 million units twice daily, rIL2 will be discontinued until the platelet count reaches 100,000/mm 3 and then resumed at a dose of 2 million units twice daily. If the platelet count then remains above 100,000 /mm 3 , this dose will be continued until the end of study. If the platelet count falls again to $\leq 100,000$ /mm 3 while on the reduced 2 million unit twice daily dose, rIL2 will be permanently discontinued.
- Should the platelet count decrease to $< 50,000$ /mm 3 , rIL-2 will be permanently discontinued.

E.1.5. AST and ALT Abnormalities

Participants who develop AST or ALT elevations will be referred for treatment by a qualified healthcare professional. Volunteers with AST or ALT levels $> 2.5 \times$ ULN at screening will be excluded.

- Volunteers with cirrhosis, severe liver disease, or active hepatitis B or C infection will be excluded from the study.
- Should AST or ALT values rise to $> 3 \times$ ULN, rIL-2 will be interrupted. rIL-2 may be resumed at 3.5 million units twice daily when AST or ALT fall to $< 2 \times$ ULN. If AST and ALT values then remain below $3 \times$ ULN, this dose will be continued to the end of study.
- If AST or ALT values rise again to $> 3 \times$ ULN while on the reduced dose of 3.5 million units twice daily, rIL-2 will be interrupted until AST and ALT fall to $< 2 \times$ ULN and then resumed at a dose of 2 million units twice daily. If AST and ALT values then remain below $3 \times$ ULN, this dose will be continued to the end of study. If AST or ALT levels rise again to $> 3 \times$ ULN while on the reduced 2 million unit twice daily dose, rIL2 will be permanently discontinued.
- If ALT values rise again to $> 3 \times$ ULN while the patient is receiving 2 million units twice daily, rIL-2 will be discontinued permanently.
- Should AST or ALT values rise to $> 5 \times$ ULN, rIL2 will be permanently discontinued.

E.1.6. Thyroid Test Abnormalities

Participants who develop thyroid function test (TFT) abnormalities will be referred for treatment by a qualified healthcare professional. Volunteers with abnormal TFTs or levels of anti-thyroid antibodies (anti-Tpo) at screening will be excluded.

- If a participant develops a TSH level $> 3.98 \text{ mIU/L}$, rIL-2 will be permanently discontinued.
- If T3 or T4 levels are outside the normal reference range of the laboratory, rIL-2 will be permanently discontinued.

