I.6.1.3. Risk Mitigation Strategy for Thromboembolic Disease

In the ESPRIT trial but not among participants in the SILCAAT trial, there was an increased occurrence of vascular events (but not in cardiac disorders) that were seen among 40 of 466 patients receiving IL-2 plus ART and 14 of 386 receiving ART alone. The most frequent vascular event was deep vein thrombosis seen in 10 IL-2 plus ART recipients and in 2 ART alone recipients. To mitigate risk for vascular events in this trial, persons with a history of venous thrombosis will be excluded from participation and at each visit, signs and symptoms of venous thrombosis will be sought.

I.6.1.4. Risk Mitigation Strategy for Laboratory Abnormalities

I.6.1.4.1. Neutropenia

The risk mitigation plan for neutropenia includes:

- Participants with an ANC <1500 cells/mm³ will not be permitted to enroll in the study;
- ANC will be measured at each clinic visit
- Should the ANC decrease to ≥500 but ≤1,000 cells/mm³, the rIL-2 dose will be interrupted until the ANC is >1,000 cells/mm³ and then rIL-2 will be restarted at 3.5 million units twice daily. If the ANC remains above 1,000 cells/mm³, this dose will be continued until the end of the study.
- Should the ANC decrease ≥500 but ≤1,000 cells/mm³ while on the reduced dose of 3.5 million units twice daily, rIL2 will be discontinued until the ANC reaches 1,000 cells/mm³, and then resumed at a dose of 2 million units twice daily. If the ANC then remains above 1,000 cells/mm³, this dose will be continued until the end of study. If the ANC falls again to ≤1,000 cells/mm³ while on the reduced 2 million unit twice daily dose, rIL2 will be permanently discontinued.
- Should the ANC decrease to <500 cells/mm³, rIL_2 will be discontinued.

I.6.1.4.2. Thrombocytopenia

The risk mitigation plan for thrombocytopenia includes:

- Participants with a platelet count <150,000/mm³ will not be enrolled in the study;
- Platelet counts will be measured at each clinic visit;
- Should the platelet count decrease to ≥50,000 but ≤100,000/mm³ the rIL-2 dose will be interrupted until the platelet count is >100,000/mm³ and then IL-2 will be restarted at 3.5 million units twice daily. If the platelet count remains above 100,000 /mm³, this dose will continue until the end of the study.

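### Section C.5.2 lets a reduced rIL-2 dose be raised again, sections E.1 and I.6.1.4 hold it for four laboratory toxicities, and the protocol does not say which rule prevails

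*Combined protocol and SAP*

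**What the plan says.** **Section C.5.2 (Guidelines for Dosage Modification).** After an interruption for a dose-limiting toxicity, treatment resumes at a dose lowered by at most 1.5 MIU per injection. If the participant then gets through a cycle at the lower dose without important toxicity, "escalation of the rIL-2 dose at the next cycle may occur by an increment of up to 1.5 MIU/dose". On particular adverse events, C.5.2 says only: "An outline of criteria for certain specific potential adverse events are provided in section E.1".

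**Section E.1, opening sentence.** "The Guidelines for Dose Modification, (protocol section C.5.2), apply to all of the scenarios listed in this section".

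**Sections E.1.3 (neutropenia) and E.1.4 (thrombocytopenia).** After the first qualifying fall and recovery, "rIL-2 will be restarted at 3.5 million units twice daily"; if the count then holds, "this dose will be continued until the end of study". A second fall leads to 2 million units twice daily, with the same instruction to keep that dose.

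**Sections E.1.5 (AST/ALT) and E.1.7 (creatinine).** The steps are again 3.5 and then 2 million units twice daily, and if the value stays within its limit, "this dose will be continued to the end of study".

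**Section I.6.1.4 (risk mitigation for laboratory abnormalities).** The same hold rule is repeated for these four toxicities, for example for neutropenia: "this dose will be continued until the end of the study".

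**The concern.** One participant can meet both conditions at once: a tolerated cycle at the reduced dose, with the laboratory value back within its limit. C.5.2 then offers a step up at the next cycle, while E.1 and I.6.1.4 say the reduced dose is kept to the end. Two participants with the same laboratory toxicity could be handled differently, one going back to the dose at which it occurred and the other not, depending on which section the site consulted. If the dose is raised, the protocol does not let anyone decide whether that is a deviation.

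The question comes up before each cycle, because C.5.1.2 normally has all eight doses prepared and handed over on day 0. It also touches the rationale: I.6.1 justifies eight cycles by the aim of reaching an exposure like that in the earlier cross-sectional study.

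**Working it through.** The plan states no figure to reproduce here. The check compares the texts and then illustrates the size.

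**1. Do the rules meet on the same doses?** The starting dose is 5 MIU (C.5.1.1) and the full C.5.2 step is 1.5 MIU.
- Down: 5 − 1.5 = 3.5 and 3.5 − 1.5 = 2. These are the two reduced doses in E.1.
- Up: 3.5 + 1.5 = 5 and 2 + 1.5 = 3.5. A full C.5.2 escalation is exactly the move that E.1 and I.6.1.4 exclude.

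**2. Does anything settle precedence?**
- The opening sentence of E.1 brings C.5.2 in without exempting its escalation provision.
- C.5.2 points to E.1 for criteria but does not say that E.1 overrides it.
- E.2.2 refers the reader to E.1 and to a section C.6.2, which does not exist.
- F.3 refers back to C.5.2 and to the Manual of Operations.

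None of these states which rule governs.

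**3. Scope.** Reduced-dose hold rules appear only in E.1.3, E.1.4, E.1.5 and E.1.7, so the conflict is confined to those four toxicities.

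**4. Size of the effect on exposure (illustration).** Exposure per cycle = dose × 2 injections × 4 days:
- 5 MIU: 40 MIU per cycle
- 3.5 MIU: 28 MIU per cycle
- 2 MIU: 16 MIU per cycle

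Planned total = 8 × 40 = 320 MIU.

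Assumptions: the reduction applies from the start of a cycle, steps are the full 1.5 MIU, no doses are missed, the first cycle at the lowest dose reached is tolerated, and under C.5.2 the dose then rises one step per cycle back to 5 MIU without recurrence.

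| Scenario | Dose held (E.1) | Dose raised again (C.5.2) | Difference | Share of 320 |
|---|---|---|---|---|
| 3.5 MIU first in cycle 7 | 6×40 + 2×28 = 296 | 6×40 + 28 + 40 = 308 | 12 MIU | 3.8% |
| 3.5 MIU first in cycle 2 | 40 + 7×28 = 236 | 40 + 28 + 6×40 = 308 | 72 MIU | 22.5% |
| 3.5 MIU in cycle 2, 2 MIU in cycle 3 | 40 + 28 + 6×16 = 164 | 40 + 28 + 16 + 28 + 4×40 = 272 | 108 MIU | 33.8% |

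For a single reduction first applied in cycle *r*, the difference is (40 − 28) × (8 − *r*) = 12 × (8 − *r*) MIU. It falls to zero when *r* = 8, because no later cycle remains.

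**5. Link to the analysis.** Secondary analysis (b) in C.2.1 represents total dose by the number of cycles received. In each scenario that number is eight under both rules, so the term takes the same value while exposure differs by the amounts above.

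**The case against.** The strongest reply is that the rules never force incompatible actions. C.5.2 is a set of guidelines, presented in brief, and its escalation is optional. A site that keeps the reduced dose merely declines an option and breaches nothing. That is correct, and it limits the point: the conflict arises only when the C.5.2 option is used.

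Second, E.1 may be read as the specific rule that governs over the general one, and I.6.1.4 repeats it for the same toxicities. This is a reasonable interpretation. The opening sentence of E.1 does not exclude it, since that sentence could take effect through the rest of C.5.2 (interruption, step size, the 2 MIU floor, no extension for missed doses). But it weakens the interpretation, and no section states it.

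Third, the hold wording might mean only that no further reduction is needed while the value stays in range. The explicit reference to the end of study counts against this.

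Finally, the Manual of Operations carries further dose-modification detail and may settle the matter in practice. It is not among the documents. Even if it does, the protocol text would still disagree with itself. How often sites would in fact diverge cannot be judged from what is available.

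**Conclusion.** The point stands as an internal inconsistency between stated dosing rules. For four laboratory toxicities the protocol both permits and excludes a return to the dose at which the toxicity occurred, and gives no rule of precedence. It bears on participant safety and consistent handling, and should be corrected.

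The illustrated difference in exposure runs from 12 to 108 MIU (3.8% to 33.8% of plan) under the assumptions listed. The documents give no frequency for these events, so the number affected among up to 20 participants is unknown.

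Three stronger conclusions that a reader might draw are not supported:
- *That the protocol cannot be followed.* It can, by never escalating after these toxicities.
- *That the planned dose-response term changes with the rule applied.* It counts cycles, and the count does not depend on the dose given. The weakness is that this count would not capture the difference in MIU. The intent-to-treat set (at least one dose) and the on-treatment set (all eight cycles) are not defined by dose level either. The primary QVOA comparison is not invalidated, and D.3.4.8 has administered doses recorded, so exposure can be reconstructed.
- *That 72 MIU is the size of the effect.* It is one early-reduction scenario; a late reduction gives far less and two early reductions give more.

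**What to change.** Reconcile C.5.2, the opening sentence of E.1, sections E.1.3, E.1.4, E.1.5 and E.1.7, and the matching parts of I.6.1.4, so that all agree on whether re-escalation is available after these four laboratory toxicities. State which section prevails if they differ, so that it is clear when a dose change is a deviation. Check that the Manual of Operations says the same. The choice of rule belongs to the sponsor and investigators, and no view is taken on it here.

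The cost is protocol wording only; no change to sample size, visits or data collection is needed.

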All participants will receive rIL-2, 5 million units (MU) subcutaneously (SC) twice a day \times 4 consecutive days, every 8 weeks, for 8 cycles in addition to ART.

Ideally, rIL-2 doses should be 10 – 12 hours apart, but no closer than 6 hours, and no greater than 18 hours apart.

If at any point rIL-2 is discontinued, efforts will be made to maintain follow-up for all data collection as outlined in the schedule of events.

C.2. STATISTICAL CONSIDERATIONS

C.2.1. Analytic Plan

The primary analysis will test whether the change in the size of the replication-competent reservoir, as measured by the modified QVOA assay, from baseline to two weeks after the last rIL-2 infusion is significantly different than is expected by random variation. In this intent-to-treat analysis, all participants who received at least one dose of IL-2 will be included. Secondarily, we will perform an on-treatment analysis including only the subset of participants who received all eight planned IL-2 cycles. We will use mixed effects models to estimate the effect of IL-2 treatment on the replication-competent reservoir among all participants, controlling for possible confounding factors including at a minimum CD4 T cell count at baseline and at pre-ART nadir, duration of virologic suppression, type of antiretroviral regimen at study entry, historical peak plasma HIV RNA, and demographic factors.

We will then fit the relevant models to address the following secondary objectives:

- a. Replicate the analyses above in the on-treatment population, i.e., those who received all 8 planned IL-2 cycles.
- b. In the intent-to-treat population, add a term indicating the number of IL-2 cycles each participant received. This will account for variability of total dose, and the associated parameter and its interaction to time point will provide an estimation of the effect modification expected from repeated dosing. We will assess for non-linearity of any dose effect both graphically and formally, and fit higher-order terms as suggested by those analyses, to explore whether there is a threshold effect (i.e., whether the effect size changes drastically past a given number of doses), an analysis that was not reported in the original Chun paper.

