- Delivery of pre-filled cycle doses of rIL-2 and review of handling, storage, and administration procedures
- CBC and metabolic panel
- Thyroid function tests and anti-Tpo antibodies
- CD4+ and CD8+ T cell count (both absolute and as percent of lymphocytes)
- Plasma HIV RNA level by PCR (using the locally available assay)
- PBMC will be cryopreserved for assays of immune cell phenotype and NK cell phenotype
- Plasma will be cryopreserved for single copy HIV RNA assay
- The participant will be observed as he/she administers the dose of rIL-2 (approximately 5 million units) subcutaneously.

D.2.6. rIL-2 Treatment Cycles 4 and 8, Day 7

Participant returns to clinic for:

- Interval history and complete physical examination.
- Concomitant medication review
- Tolerance and compliance with injection schedule
- CBC and metabolic panel
- CD4+ and CD8+ T cell count (both absolute and as percent of lymphocytes)
- Plasma HIV RNA level by PCR (using locally available assay)
- PBMC will be cryopreserved for assays of immune cell phenotype and NK cell phenotype
- Plasma will be cryopreserved for single copy HIV RNA assay

D.2.7. rIL-2 Treatment Cycles 2 and 3, Day 0

NOTE: Each treatment cycle should begin 7-10 weeks after start of last treatment cycle. These visits will include:

- Interval history and targeted physical examination, including weight.
- Concomitant medication review.
- Delivery of pre-filled cycle doses of rIL-2 and review of handling, storage, and administration procedures

- CBC and metabolic panel
- Thyroid function tests and anti-Tpo antibodies
- CD4+ and CD8+ T cell count (both absolute and as percent of lymphocytes)
- Plasma HIV RNA level by PCR (using the locally available assay)
- IL-2 immunogenicity (cycle 2 only)

D.2.8. rIL-2 Treatment Cycles 5, 6, and 7, Day 0

NOTE: Each treatment cycle should begin 7-10 weeks after start of last treatment cycle. These visits will include:

- Interval history and targeted physical examination, including weight.
- Concomitant medication review.
- Delivery of pre-filled cycle doses of rIL-2 and review of handling, storage, and administration procedures
- CBC and metabolic panel
- Thyroid function tests and anti-Tpo antibodies
- CD4+ and CD8+ T cell count (both absolute and as percent of lymphocytes)
- Plasma HIV RNA level by PCR (using the locally available assay)

D.2.9. rIL-2 Treatment cycles 1-8, Days 2 and 4

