Staff will contact the participant by phone to assess tolerance and compliance with injection schedule

D.2.10. End of Study Visit (or Premature Discontinuation Visit)

NOTE: The end of study visit should take place 8 weeks (+/- 2 weeks) after Day 0 of the last (8th) treatment cycle. In the case of premature discontinuation, the end of study visit should take place at least 6 weeks after day 0 of the last treatment cycle and may take place up to 10 weeks after day 0 of the last treatment cycle.

These visits will include:

- Interval history and targeted physical examination.
- Immunogenicity testing
- CD4+ and CD8+ T cell count (both absolute and as percent of lymphocytes)
- Plasma HIV RNA level by PCR (using the locally available assay)
- IL-2 immunogenicity
- At this visit the participant will undergo a 4 Liter leukapheresis at the Seidman Ambulatory Stem Cell Transplant Unit at University Hospitals using AIDS protocol 328.
- Plasma will be cryopreserved for single copy HIV RNA assay
- Leukapheresis product PBMC will be cryopreserved for:
 - HIV reservoir assay by EDITS
 - HIV reservoir assay by QVOA
 - Total and intact proviral DNA assay (Accelavir)
 - Assays of immune cell phenotype and NK cell phenotype

If leukapheresis cannot be done after premature treatment discontinuation for any reason, a 120 cc. blood draw will be obtained for preparation of PBMC and plasma. Based upon cell yield these samples will be used for:

- Plasma will be cryopreserved for single copy HIV RNA assay
- HIV reservoir assay by EDITS
- HIV reservoir assay by QVOA
- Total and intact proviral DNA assay (Accelavir)
- Assays of immune cell phenotype and NK cell phenotype

D.2.11. Immunogenicity follow-up

Participants who have detectable neutralizing antibodies at the end of study visit will be followed approximately every 90 days for repeat testing until 12 months after the end of study or until a negative result is obtained. During these visits, an interval medical history and targeted physical exam will be conducted. If clinically significant events have occurred, the participant will be referred for appropriate medical care.

D.2.12. Management of off-window visits

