Every effort should be made to conduct each visit within its allocated window. If, however, a participant cannot conduct a scheduled visit within the scheduled window, the principal investigators will determine whether the visit can be conducted within a few days outside of the per-protocol window. If conducting the visit on the proposed off-window date would raise a safety concern or could compromise the integrity of the study, the visit will not be rescheduled and will be recorded as missed. In either case, the reasons for the off-window visit will be recorded in the source document and the protocol deviation CRF will be completed.

D.2.13. Holding rIL-2 cycles

The initiation of an rIL-2 cycle can be delayed or cancelled by the principal investigators, if deemed necessary for clinical or logistical reasons. When a cycle is delayed beyond the end of the scheduled window, the reasons for the delay or cancellation will be recorded in the source document and the protocol deviation CRF will be completed. If a cycle is cancelled, the corresponding day 2, 4, and 7 visits will also be cancelled.

D.3. INSTRUCTIONS FOR EVALUATIONS

All clinical and laboratory information required by this protocol is to be present in the source documents. Results of all approved laboratory tests performed as part of the study will be provided to the participants' physicians, and any resulting clinical action will be taken by the participant and their physician without interference from the study personnel.

D.3.1. Documentation of HIV

For the purposes of this protocol, any combination of two positive results of the following tests is sufficient for documentation of HIV infection: a) FDA-approved HIV ELISA or EIA; b) FDA-

approved HIV Western blot; c) FDA-approved HIV rapid test; d) p24 antigen immunoassay; e) FDA-approved nucleic acid test; f) detectable HIV RNA in plasma by an FDA-approved method.

D.3.2. Medical History

The medical history must include all diagnoses that were either established within 45 days prior to or ongoing at the time of enrollment. Any allergies to any study medications and their formulations must be documented. All elements of the medical history will be recorded on the source documents.

D.3.3. Medication History

A medication history must be present, including start and stop dates. The table below lists the medications that must be included in the history to be recorded in the source documents.

Table 1. Medications to be recorded

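### For early stoppers, the only post-treatment QVOA sample is timed from the last cycle given, so a stop decided after a hold or cancelled cycle can fall after the window has closed

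*Combined protocol and SAP*

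**What the plan says.** QVOA material is collected at two points only: the pre-treatment leukapheresis (D.2.2) and the end-of-study or premature-discontinuation visit (D.2.10). The cycle 1 Day 7 visit stores cells for EDITS and phenotyping, and the Day 7 visits of cycles 4 and 8 store cells for phenotyping. None stores cells for QVOA.

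The timing rules are these:

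- **Completers (D.2.10):** "The end of study visit should take place 8 weeks (+/- 2 weeks) after Day 0 of the last (8th) treatment cycle".
- **Early stoppers (D.2.10):** the upper limit is that the visit "may take place up to 10 weeks after day 0 of the last treatment cycle". The lower limit is 6 weeks, counted from the same Day 0. If leukapheresis cannot be done, a 120 cc blood draw replaces it. No separate timing is given for that draw.
- **Next cycle (D.2.7 and D.2.8, with a similar note in D.2.5):** "Each treatment cycle should begin 7-10 weeks after start of last treatment cycle".
- **Holds (D.2.13):** "The initiation of an rIL-2 cycle can be delayed or cancelled by the principal investigators". The section foresees the case "When a cycle is delayed beyond the end of the scheduled window" and asks for a deviation form. It sets no maximum delay.
- **Off-window visits (D.2.12):** the principal investigators decide whether a visit can take place slightly outside its window. If the proposed date raises a safety or study-integrity concern, "the visit will not be rescheduled and will be recorded as missed".
- **After a treatment stop (C.1):** "efforts will be made to maintain follow-up for all data collection as outlined in the schedule of events".

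C.2.1 puts everyone with at least one dose into the primary analysis. It does not say how a missing post-treatment QVOA value is handled.

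**The concern.** The early-stopper window is anchored to the wrong event. The next cycle may start as late as week 10, and the sampling window also closes at week 10. While a participant is on hold, nobody yet knows that the last cycle given was the final one, so nothing triggers the end-of-study visit. If the hold ends in a permanent stop, the window may already have closed, and no rule reopens it at the decision.

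What is at stake is the primary endpoint in particular people. Those held or stopped for toxicity have received fewer cycles, so losing their samples is related to exposure and tolerance. A participant with only a baseline value can stay in a mixed model but tells it nothing direct about his or her own change. The loss also thins out the low-exposure end of the number-of-cycles analysis planned in C.2.1(b).

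**Working it through.** **Windows, in weeks after Day 0 of the last cycle given**

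1. Completers: 8 - 2 = 6 to 8 + 2 = 10. Early stoppers: 6 to 10. The two windows agree.
2. Next cycle: weeks 7 to 10. If the stop is decided at that Day 0 visit, the time left for sampling is 10 - 7 = 3 weeks, 10 - 8 = 2, 10 - 9 = 1, or 10 - 10 = 0. A stop decided at week 7 or 8 can still meet the window.
3. Held cycle: if a participant is held at week 8 and the permanent stop is decided at, say, week 12, the window closed 12 - 10 = 2 weeks earlier.
4. Cancelled cycle, then a stop at the following Day 0: 2 x 7 = 14 to 2 x 10 = 20 weeks. This assumes that the cancelled cycle keeps its place in the 7-10 week spacing, since D.2.13 does not say. The excess over the limit is 14 - 10 = 4 to 20 - 10 = 10 weeks, well beyond the short allowance in D.2.12.

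**How a hold can outlast week 10.** Holds in E.1.1 (infection), E.1.3 to E.1.7 except thyroid (laboratory values) and E.1.9 (zoster) end on recovery, not on a date. D.2.13 adds delays for clinical or logistical reasons.

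**What lost pairs would cost in power (background only)**

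The inputs are the difference of 0.64 IUPM and the variance of 0.41 in C.2.2. Two-sided alpha of 0.05 is my assumption, because none is stated. A normal approximation with no within-person correlation gives

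n = 2 x 0.41 x (1.960 + 0.842)² / 0.64² = 15.7, rounded up to 16.

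This reproduces the synopsis figure of 16. C.2.2 gives 20 for the same power.

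For a paired t-test I take the SD of change as √(2 x 0.41 x (1 - r)), where r is the within-person correlation:

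| Evaluable pairs | r = 0 | r = 0.3 | r = 0.5 |
|---|---|---|---|
| 20 | 0.850 | 0.947 | 0.989 |
| 18 | 0.807 | 0.921 | 0.979 |
| 16 | 0.753 | 0.884 | 0.962 |

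The losses of 2 and 4 pairs are illustrations, not predictions. At moderate correlation the power cost is slight, so selective loss is the firmer argument.

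**The case against.** The strongest reply is that few people will reach this gap. Phone calls on Days 2 and 4 of every cycle, and Day 7 visits in cycles 1, 4 and 8, will prompt many stops while the whole window is still open. A.5 says that most toxicities resolve within 5 days of completing a cycle. Under E.1, a participant held for neutrophils, platelets, transaminases or creatinine resumes on recovery, and the recurrence-based permanent stop comes only after treatment has resumed; a new cycle then gives a new Day 0. A hold that ends directly in a stop needs non-recovery, worsening off drug, investigator discretion or a participant's request. All of this stands, and it limits the point to a subset.

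A reader might go further than the documents allow in four ways:

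- **A headcount from the thyroid figure.** The 10-15% in A.5 is an informal estimate of thyroid dysfunction in two earlier trials. It is not a rate of late stops. E.1.6 makes a thyroid abnormality an immediate permanent stop with no hold.
- **Laboratory turnaround as the main route.** Pre-cycle bloods are drawn at the Day 0 visit at which doses are delivered, and no section says that dosing waits for results. If dosing starts, that cycle becomes the last one and the window restarts.
- **Automatic loss.** D.2.10 is worded as guidance, and D.2.12 records a visit as missed only on a safety or integrity concern. The remaining gap is that D.2.12 has no provision for a visit that is weeks late.
- **A stopper sampled at the nominal end of the eight-cycle schedule.** C.1 promises only efforts to follow a schedule held in the Manual of Operations, which was not available here. D.2.10 covers premature discontinuation specifically. A clarifying sentence in C.1 is worthwhile, but there is no demonstrated conflict.

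**Conclusion.** The concern holds for participants whose permanent stop is decided after a hold or a cancelled cycle. For them the only post-treatment QVOA visit can already be out of window: by 2 weeks in the week-12 example, and by 4-10 weeks after one cancelled cycle. The plan then offers no clear way to collect the sample. How many of the 20 this would touch cannot be worked out from the documents.

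The conclusion rests on two readings: that the early-stopper window runs from the last cycle actually given, as D.2.10 is worded, and that the Manual of Operations contains no rule that reopens it. Because the primary analysis includes everyone dosed and has at most 20 people, a cheap correction is justified even if few are affected.

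**What to change.** - **D.2.10:** keep the 6-week minimum. Set the upper limit to the later of 10 weeks after Day 0 of the last cycle given and 4 weeks after the permanent-stop decision. A stop at week 7 would then allow sampling to week 7 + 4 = 11. A stop at weeks 14-20 would allow it to weeks 18-24.
- **D.2.10 and D.2.12:** state that this sample, by leukapheresis or the 120 cc draw, is still collected when late unless there is a safety concern, and is not recorded as missed for timing alone.
- **C.1:** state that participants who stop treatment give the post-treatment QVOA sample at this visit.
- **C.2.1:** record weeks since last dose, and report the primary model with and without samples taken after week 10.

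The cost is wording and one derived variable. No procedure is added, and no dose, hold or stopping rule changes. The downside is that a few samples will be taken later and at more variable times after the last dose. Since holds have no maximum, that lateness has no fixed bound, and the sensitivity analysis on a handful of samples will be imprecise.

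While editing, the authors should also reconcile C.2.1, which times the primary change at two weeks after the last rIL-2, with the 6-10 week sample in D.2.10. That is a separate matter and affects every participant.
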